9.1.2 Initial Sample Size Calculation

Prior to protocol version 2.1, the initial study sample size was calculated for both populations. We expected that 60% of our patients would be imaged for recurrent disease after surgery and/or radiation therapy, and we expected that 40% of our patients would be imaged prior to initial therapy for glial malignancy.

Population 1: Initially, the study's primary endpoint was misclassification rate as our statistical endpoint, defined as the percentage of patients that are classified incorrectly as either recurrent disease and treatment related changes (ie misclassification rate = $[FP+FN]/[FP+FN+TP+TN]$).

True positive (TP): FET PET read as positive for tumor, pathology/follow-up demonstrates tumor recurrence in at least one biopsy sample.

False positive (FP): FET PET read as positive for tumor, pathology/follow-up negative tumor recurrence in none of the biopsy samples.

True negative (TN): FET PET read as negative for tumor, pathology/follow-up negative tumor recurrence in none of the biopsy samples.

False negative (FN): FET PET read as negative for tumor, pathology/follow-up demonstrates tumor recurrence in at least one biopsy sample.

The sample size was calculated based on three subpopulations:

1. **Recurrent metastatic disease:** We estimated that there would be a prevalence of 65% for recurrent metastatic tumor at time of imaging. Papers that estimate misclassification rate have shown a misclassification rate of 24% (sensitivity of 86.7%, specificity of 68.2%, and a prevalence of 43%) for perfusion MRI (9), a misclassification rate of 46% (sensitivity of 59%, specificity of 41%, and a prevalence of 75%) for lesion quotient MRI. For FET PET, the literature has shown a misclassification rate ranging from 7 to 17%:
 - Misclassification rate of 17% with a sensitivity of 83%, specificity of 85% and prevalence of 84% (10).
 - Misclassification rate of 7% with a sensitivity of 95%, specificity of 91% and prevalence of 48% (11).

For our sample size analysis, we used a binomial test for proportions. Assuming a misclassification rate of 35% for conventional MRI and 10% for FET PET, 34 patients needed to be imaged with pathologic correlation to demonstrate the difference with a significance level of 0.01 with a power of 90%, and a one-sided test. Our null hypothesis was that there is no difference between MRI and FET PET misclassification rates (H_{null} : MRI_misclass = FET PET misclass = 35%). The alternative hypothesis was that the FET PET misclassification rate is lower (H_{alt} : FET PET misclass < MRI_misclass = 35%). We estimated that 55% of patients would have pathology as a correlate, and we would replace all patients who did not have pathology within four weeks of imaging to fill our primary endpoint. Therefore the total patient population in population 1 with metastatic lesions was 62 patients.

2. **Recurrent high-grade glioma (Grade 3 and 4):** Based on prior data from UCSF, we anticipated that 70% of patients would have recurrent tumor at the time of imaging (12). Using this same paper as an estimate of misclassification rate using MRI for the characterization of recurrent tumor, resulted in a sensitivity of 82%, specificity of 76%, prevalence of 70% and a misclassification rate of 19.8%. For FET PET, the first paper to publish the sensitivity and specificity of FET PET was Rachinger et al in 2005; they reported a sensitivity, specificity and misclassification rate of 100%, 93% and 2% respectively (45 patients with a prevalence of 69%) (13). A subsequent paper published in 31 patients, 26 of whom had recurrent tumor, had a sensitivity of 100% and a specificity of 84%, resulting in a misclassification rate of 2.6% (14). A third paper looked at the ability to characterize pseudoprogression after radiochemotherapy all of whom had an enhancing lesion on MRI, demonstrated a sensitivity, specificity and misclassification rate of 100%, 91% and 5% respectively (6). No meta-analysis exists for estimating the accuracy of FET PET, and therefore we have selected 5% as a reasonable goal misclassification rate. Our null hypothesis was that there is no difference between MRI and FET PET misclassification rates (19.8% for MRI and 5% for FET PET). For our sample size analysis, we used a binomial test for proportions. Therefore, 27 patients needed to be imaged with pathologic correlation to demonstrate the difference with a significance level of 0.05 with a power of 80%, and using a one-sided t-test. Our null hypothesis was that there is no difference between MRI and FET PET misclassification rates (H_{null} : MRI_misclass = FET PET misclass = 19.8%). The alternative hypothesis was that the FET PET misclassification rate is lower (H_{alt} : FET PET misclass < MRI_misclass = 19.8%). We estimated that 40% of patients would have pathology as a correlate, and we would replace all patients who did not have pathology within four weeks of imaging to fill our primary endpoint. Therefore the total patient population in population 1 with high grade gliomas was 68 patients.

- 3. Recurrent low-grade glioma (Grade 1 and 2):** We included this population as a secondary endpoint in order to gain information on the role of FET PET in the characterization of low-grade gliomas. We aimed to image 20 patients as part of this cohort to obtain preliminary information about the role of FET PET in this population.

Population 2: For population 2 we selected a misclassification rate for the characterization of tumor as either low or high grade. Most of the data on the literature for the effectiveness of conventional imaging (MRI) for the classification of disease is reported as sensitivity and specificities; the best meta-analysis available suggests that MR spectroscopy has a sensitivity of 75% and a specificity of 70% (15). In this meta-analysis of 25 studies, there were 427 low-grade and 802 high-grade tumors, resulting in a prevalence of 65% for high-grade tumors. Assuming a prevalence of 65%, this would imply a misclassification rate of 27% for conventional imaging. Using a recent FET PET article that demonstrated a sensitivity and specificity of 100% and 73% respectively for the characterization of low-grade and high-grade gliomas with a prevalence of 52%, we estimated a misclassification rate of roughly 13% for FET PET (16). Therefore, our target misclassification rate was 13%. Our null hypothesis was that there is no difference between MRI and FET PET misclassification rates (27% for MRI and 13% for FET PET). For our sample size analysis, we used a binomial test for proportions. Therefore, 49 patients needed to be imaged with pathologic correlation to demonstrate the difference with a significance level of 0.05 with a power of 80%, using a one-sided test. Our null hypothesis is that there is no difference between MRI and FET PET misclassification rates (H_{null} : $\text{MRI_misclass} = \text{FET PET misclass} = 27\%$). The alternative hypothesis is that the FET PET misclassification rate is lower (H_{alt} : $\text{FET PET misclass} < \text{MRI_misclass} = 27\%$).

We estimated that 50 patients with intracranial neoplasms would be enrolled each year, and we estimated that we would enroll 199 patients over the four years of the study.

9.2 Analyses Plans

9.2.1 Analysis Populations

There will be two analysis populations. The first population will be patients with intracranial neoplasm (both glial and metastatic disease) previously treated with surgery and/or radiation therapy where there is concern for recurrent disease. The second population will be patients with suspicion or known glial malignancy planning on undergoing biopsy or surgery.

The safety analysis dataset will include all patients who completed initial FET PET imaging per protocol.

The efficacy analysis dataset will include all glioma patients who completed initial FET PET imaging per protocol (repeat FET PET imaging is excluded). FET PET scans that are not readable due to data or scanner errors will be excluded from efficacy analyses.

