2.2 Secondary Objectives

| Secondary Objectives | Endpoints | Time Frame |
|--|---|-----------------|
| 1. To determine if FET PET can differentiate between benign TRC and recurrent glioma in comparison to a histopathological standard of truth. | 
 • Sensitivity of FET PET using a histopathology standard of truth (subject- and lesion-level) • Specificity of FET PET using a histopathology standard of truth (subject and lesion-level) • Positive Predictive Value (PPV) of FET PET using a histopathology standard of truth (subject and lesion-level) • Negative Predictive Value (NPV) of FET PET using a histopathology standard of truth (subject and lesion-level) • Accuracy of FET PET using a histopathology standard of truth (subject and lesion-level) • Misclassification Rate of FET PET using a histopathology standard of truth (subject and lesion-level) | Up to 6 months. |
| 2. To determine if FET PET can differentiate between benign TRC and recurrent glioma in comparison to a CSOT evaluated using estimates other than subject-based sensitivity and specificity. | 
 • Sensitivity of FET PET using a CSOT (lesion-level) • Specificity of FET PET using a CSOT (lesion-level) • PPV of FET PET using a CSOT (subject and lesion-level) • NPV of FET PET using a CSOT (subject and lesion-level) • Accuracy of FET PET using a CSOT (subject and lesion-level) • Misclassification Rate of FET PET using a CSOT (subject and lesion-level) | Up to 6 months. |

| Secondary Objectives | Endpoints | Time Frame |
|---|--|-----------------|
| 3. To assess the safety of FET PET, as determined by treatment emergent adverse events (TEAEs) within 48 hours of FET administration. | Incidence of treatment-emergent adverse events (TEAEs) | Up to 48 hours. |
| 4. To describe the inter-reader variability between 3 independent blinded readers of FET PET images in their assessments of benign TRC versus recurrent glioma. | Fleiss' kappa | N/A |
| 5. To describe intra-reader variability between 3 independent blinded readers of FET PET images in their assessments of benign TRC versus recurrent glioma. | Cohen's kappa | N/A |

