3.5 Discontinuation of Study Intervention

Study drug will be given per protocol, unless any of the following discontinuation criteria are met:

- Unacceptable adverse event(s);
- Participant decides to discontinue study drug (with or without concurrent withdrawal of informed consent);
- Significant participant non-compliance with protocol;
- If the participant meets an exclusion criterion (either newly developed or not previously; or, recognized) that precludes further study drug administration.
- General or specific changes in the participant's condition render the participant unacceptable for study drug administration in the judgment of the investigator.

Participants will be discontinued from study drug administration when any of these criteria apply. The reason for discontinuation, and the date the participant discontinued (defined as the later date of decision to discontinue drug or last dose) must be documented in the case report form (CRF). Participants removed from study for unacceptable adverse events will be followed as described in Section 7.3. Participants who do not receive study drug will be replaced.

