5.2 Dosage and Administration

The imaging agent (FET) will be administered on an outpatient basis. It will be administered intravenously within the PET scanner at the time of imaging. The nominal injected dose will be 4 to 7 mCi \pm 10% of FET per imaging time point. Pediatric doses will be adjusted based upon the patient's weight (dose = [(patient weight in kg)/70 kg] x adult dose). The maximum dose will be 7 mCi, adjusted by weight.

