5.2.1 Other Modalities or Procedures

5.2.1.1 PET Imaging

Participants may undergo sedation as required in order to successfully undergo imaging. Sedation or anesthesia will be administered per institutional protocol.

Study participants will undergo the FET PET imaging after all screening and baseline assessments have been completed. The radiopharmaceutical will be administered while the

patient is in the PET scanner, and imaging will last for 40 minutes. Acquired PET data will be reconstructed so that three time points are created:

1. Perfusion: 60-second acquisition that starts immediately when activity is noted in the field of view.
2. Equilibrium: 10-minute acquisition acquired between 10 and 20 minutes after injection.
3. Washout: 10-minute acquisition acquired between 30 and 40 minutes after injection.

Additionally, a 20 minute acquisition will be reconstructed between 20 and 40 minutes after injection to match the analysis performed in Lohmann et al (8).

Each study will be reviewed by a board-certified nuclear medicine physician and neuroradiologist within seven working days of the completion of the study, and a formal report will be dictated. This will be performed separately from the final analysis. The imaging findings on FET PET will be provided to the neurosurgeon and can be used in addition to MRI for planning of biopsy and surgery. For patients who received subsequent surgery, if possible the multi-parametric imaging examination will be used to target 1-4 tissue samples that have distinct metabolic findings for distinguishing recurrent disease from treatment effects.

If imaging is performed on a PET/MRI, a gadolinium-based contrast will be administered. The patient's eGFR will be checked and gadolinium will be administered per radiology department guidelines. The MRI protocol will include the clinical standard MRI. The MRI protocol may also contain research sequences such as novel sequences used for attenuation correction on PET/MRI (ie ZTE or zero echo time) and MRI spectroscopy sequences.

Optional repeat FET PET imaging will be offered to adult patients.

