5.3 Monitoring and Toxicity Management

Each patient receiving FET will be evaluable for safety. The safety parameters include vital signs (heart rate and blood pressure) as well as physical findings and spontaneous reports of adverse events reported to the investigator by patients.

6 Study Procedures and Observations

Screening assessments must be performed within 30 days prior to the first dose of investigational product. Any results falling outside of the reference ranges may be repeated at the discretion of the investigator. Treatment or visit delays for public holidays or weather conditions do not constitute a protocol violation.

A written, signed, informed consent form (ICF) and a Health Insurance Portability and Accountability Act (HIPAA) authorization must be obtained before any study-specific assessments are initiated. A copy of the signed ICF will be given to the subject and a copy will be filed in the medical record. The original will be kept on file with the study records.

REDCap will be used to collect data for this study. REDCap is a secure, HIPAA-compliant, web-based system.

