6.1.3 Optional Study Procedures - Imaging

Optional repeat FET PET imaging will be offered to adult patients. Repeat procedures include:

- FET administration and adverse event evaluation
 - Evaluation of adverse events 20 min after completion of imaging, \pm 60 min

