7.1 Definitions

7.1.1 Evaluable for Toxicity

All patients will be evaluable for toxicity from the time of FET administration.

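### The safety dataset is defined by completing the first scan, not by receiving FET, so a patient whose reaction ends that scan drops out of the TEAE incidence

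*Combined protocol and SAP*

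**What the plan says.** Section 9.2.1 (Analysis Populations) gives the only definition of the safety set: "The safety analysis dataset will include all patients who completed initial FET PET imaging per protocol". The efficacy set in the same section uses nearly the same completion condition, restricted to glioma patients.

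Two other sections define safety evaluability by exposure. Section 5.3: "Each patient receiving FET will be evaluable for safety". Section 7.1.1: "All patients will be evaluable for toxicity from the time of FET administration".

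The endpoint is secondary objective 3 in Section 2.2: "To assess the safety of FET PET, as determined by treatment emergent adverse events (TEAEs) within 48 hours of FET administration".

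On timing, Section 5.2 says of the tracer: "It will be administered intravenously within the PET scanner at the time of imaging". Section 5.2.1.1 adds that it is given while the "patient is in the PET scanner, and imaging will last for 40 minutes".

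On repeat scans, Section 6.1.3 says: "Optional repeat FET PET imaging will be offered to adult patients". That section and Appendix 1 both schedule an adverse event evaluation at the repeat scan.

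**The concern.** A safety denominator should be fixed by exposure. Here it depends on something that happens after exposure and that an adverse event can itself prevent. Section 3.5 lists an unacceptable adverse event among the reasons for stopping study drug, so the protocol foresees adverse events that interrupt participation. An acute reaction that ends the scan is the kind of event a tracer safety summary should show, and under the wording of 9.2.1 it leaves both the numerator and the denominator.

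The stake is the published TEAE incidence. Section 1.1 gives the study's aim as safety and efficacy data for a New Drug Application. If events are rare, leaving out one or two patients can decide whether the table shows none or some.

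**Working it through.** **Step 1. Set the rules side by side for one patient.** The patient is injected in the scanner, reacts, and is taken out before 40 minutes.

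| Provision | Is the patient counted? |
|---|---|
| 5.3, each patient receiving FET | Yes |
| 7.1.1, evaluable from administration | Yes |
| 2.2, objective 3, TEAE within 48 hours of administration | Yes, the event is in the window |
| 9.2.1, safety analysis dataset | No, the first scan was not completed |

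I looked for a provision that overrides 9.2.1 and found none. Section 9.2.3 (secondary endpoints) describes no TEAE analysis. The replacement rule in 3.5 covers only participants who never receive drug.

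**Step 2. Direction of the bias.** Let N be the number injected and E the number of them with a TEAE. Among non-completers, let k have a TEAE and m have none.

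- Incidence by exposure: E/N.
- Incidence under 9.2.1: (E − k)/(N − k − m).
- The second is lower than the first when N(E − k) < E(N − k − m), which simplifies to k/(k + m) > E/N.

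The rule therefore understates incidence when TEAEs are more frequent among non-completers than among all injected patients. It overstates incidence when they are less frequent.

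**Step 3. Illustration.** The plan states no figure to reproduce. N = 199 is the anticipated enrolment in Section 3.3, and I assume that all 199 are injected. The values of k and m and the events among completers are also assumptions. Intervals are exact (Clopper-Pearson) 95%: the lower limit is the 0.025 quantile of Beta(x, n − x + 1) and the upper limit the 0.975 quantile of Beta(x + 1, n − x). For x = 0 the upper limit is 1 − 0.025^(1/n).

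No TEAE among completers, m = 0:

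| k | Under 9.2.1 | By exposure |
|---|---|---|
| 1 | 0/198 = 0%, upper limit 1.8% | 1/199 = 0.5% (0.01% to 2.8%) |
| 2 | 0/197 = 0%, upper limit 1.9% | 2/199 = 1.0% (0.1% to 3.6%) |
| 4 | 0/195 = 0%, upper limit 1.9% | 4/199 = 2.0% (0.6% to 5.1%) |

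Two TEAEs among completers:

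- k = 2, m = 0: 2/197 = 1.0% instead of 4/199 = 2.0%.
- k = 0, m = 10: 2/189 = 1.06% instead of 2/199 = 1.01%, so the bias is upward but small.
- k = 1, m = 10: 2/188 = 1.06% instead of 3/199 = 1.51%. One event-driven stop outweighs ten event-free ones, because 1/11 = 9.1% exceeds 1.51%.

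**The case against.** **The bias has no fixed sign.** A reader might infer that the rule always flatters the product. The documents do not support that. The rule drops every non-completer, and scans may also stop because the patient cannot tolerate the exam (foreseen in 3.4.2), decides to stop, or does not comply (3.5). Losing such patients without an event raises incidence, as in the case k = 0, m = 10. This objection stands. What remains is that event-driven stops push incidence down.

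**Repeat scans are not excluded from safety.** A reader might infer from the word for the first scan in 9.2.1 that events after repeat injections are left out. The sentence says which patients enter the set, not which administrations count. Section 9.2.1 expressly excludes repeat imaging for efficacy only, and objective 3 is not limited to the first administration. The fair statement is that their handling is unspecified.

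**Safety oversight is not lost.** Adverse event recording, follow-up and expedited reporting (Sections 7.2 to 7.4 and Appendix 2) do not depend on 9.2.1. The patient is missing from the analysis set, not from surveillance. A patient whose event begins after a completed first scan also stays in the set. Both points stand and narrow the concern.

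**The endpoint is secondary and descriptive.** It has no test or threshold, and study success does not depend on it. That limits the consequence, but it does not resolve the contradiction or make completion a suitable condition for a safety denominator.

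**Conclusion.** The concern holds in this form: 9.2.1 contradicts 5.3 and 7.1.1 and, applied as written, omits from TEAE incidence an injected patient whose reaction ends the first scan. This is a stated rule that gives a wrong result, not a missing detail.

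The size cannot be derived from the documents, which give no rate of non-completion or of acute reactions. The 0/198 against 1/199 comparison shows the mechanism and is not a forecast. It assumes that all 199 planned patients are injected, that no completer has a TEAE, and that exactly one reaction ends a scan. The upper limit of 1.8% mainly reflects the sample size. What the omission changes is the point estimate, from 0.5% to 0%, and the upper limit, from 2.8% to 1.8%.

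**What to change.** Replace the safety sentence in 9.2.1 with a definition by exposure, for example: *Safety analysis dataset: every patient given any amount of FET, whether or not imaging was completed.* Leave the completion condition in the efficacy definition, where it concerns readable images.

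Add a sentence stating that TEAEs after optional repeat administrations are included in the safety analysis.

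One related gap should be closed at the same time. Section 6.1.1 and Appendix 1 time the scheduled adverse event evaluation from the end of imaging, so a patient who does not finish has no defined time for it. The plan should say how that evaluation is anchored for such a patient.

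The cost is a few lines of text. The reported TEAE rate may come out slightly higher. The primary analysis and its sample size are untouched.

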1.3 Patient Population

Patient population 1: Patients with intracranial neoplasms (glial or metastatic disease) with concern for recurrence or progression on conventional imaging (e.g., MRI). This population will be broken into three groups:

1. Recurrent metastatic lesions
2. Recurrent high-grade gliomas (Grades 3 and 4)
3. Recurrent low-grade gliomas (Grades 1 and 2)

Patient population 2: Patients with suspected glial neoplasms (Grade 2-4) planning to undergo biopsy or surgery prior to primary treatment (radiation therapy and/or surgery).

2 Objectives of the Study

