2.1 Primary Objective

| Primary Objective | Endpoints | Time Frame |
|--|---|-----------------|
| 1. To determine if FET PET can differentiate between benign treatment-related changes (TRC) and recurrent glioma in comparison to a composite standard of truth (CSOT) that includes pathology and other clinical information, evaluated using estimates of sensitivity and specificity. | 
• Sensitivity of FET PET using a CSOT (subject-level)• Specificity of FET PET using a CSOT (subject-level) | Up to 6 months. |

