3.4.1 Inclusion Criteria

1. Presence or suspicion of intracranial neoplasm in two populations:
 - a. Population 1: patients after primary treatment (radiation therapy and/or surgery) with suspicion of recurrence on MRI. Three sub-populations will be considered:
 - i. Recurrent metastatic lesions
 - ii. Recurrent high-grade gliomas (Grades 3 and 4)
 - iii. Recurrent low-grade gliomas (Grades 1 and 2)
 - b. Population 2: patients prior to primary treatment with planned biopsy or surgical resection.
2. Age > 3 years.

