2. The goal of this study is to characterize existing lesions on the FET PET. If new lesions develop on follow-up imaging that are not in the same location or related to the original lesion of concern at time of FET PET, this will not be characterized as recurrent disease. This same issue may exist with histopathology, where a new lesion geographically distinct from the baseline lesion may be sampled and positive for tumor, but the lesion of concern was unchanged and not biopsied. The Truth Panel will take this into account when determining the characterization of the lesion.
3. Patients without imaging or histopathology due to clinical progression (hospice and/or death) will be characterized as recurrent disease.

The CSOT of progression/recurrence (positive) or TRC (negative) will be determined for each individual lesion and for each subject overall.

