9.2.4 Exploratory Analysis

Exploratory analysis will be performed on patients with glioma who are under suspicion for progression or recurrence. For these participants, standard-of-care MRI performed during the FET PET/MRI will undergo retrospective analysis by a panel of three blinded independent neuroradiologists. The neuroradiologists will classify the findings as positive (indicating recurrence) or negative (indicating TRC) and compare them with the CSOT. The 3 readers will be blind to 18F-FET PET images, prior imaging results, clinical data, surgical reports, and histopathological results.

SUV and TBR results (SUVmean, SUVmax, SUVpeak, TBRmean, and TBRmax) will be summarized by descriptive statistics for each reader on a lesion-specific basis.

Exploratory analysis will also be performed to assess relationships between serial FET PET and clinical outcome (benign TRC and recurrence) in patients with recurrent metastatic lesion, recurrent high-grade gliomas and recurrent low-grade gliomas (Population 1).

Exploratory analyses will also be performed to determine if FET PET can differentiate between benign TRC and recurrent metastatic lesions and to determine if FET PET can accurately differentiate between low-grade and high-grade gliomas in population 2.

10 Study Management

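### As written, the efficacy dataset in Section 9.2.1 is not limited to Population 1, so it admits untreated gliomas to which recurrence versus TRC cannot apply

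*Combined protocol and SAP*

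**What the plan says.** Section 9.2.1 first names two analysis populations. The first is previously treated patients, glial or metastatic, with concern for recurrence. Of the other it says "The second population will be patients with suspicion or known glial malignancy planning on undergoing biopsy or surgery". It then defines the set for all efficacy analyses: "The efficacy analysis dataset will include all glioma patients who completed initial FET PET imaging per protocol". Repeat scans and unreadable scans are excluded; untreated patients are not mentioned.

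Section 3.4.1 fixes the treatment status: "Population 2: patients prior to primary treatment with planned biopsy or surgical resection".

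The primary objective (Section 2.1) asks whether FET PET "can differentiate between benign treatment-related changes (TRC) and recurrent glioma". The reference standard has the same two outcomes (Section 8.1.2.1): "The CSOT of progression/recurrence (positive) or TRC (negative) will be determined for each individual lesion and for each subject overall".

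Section 9.2.2 applies these definitions and adds no population limit. Section 9.2.3 uses the same efficacy set for the secondary endpoints. Population 2 has its own aim only in Section 9.2.4, "to determine if FET PET can accurately differentiate between low-grade and high-grade gliomas in population 2". The MRI analysis in that section is expressly confined to glioma patients with suspected progression or recurrence, a limit that Section 9.2.1 lacks.

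**The concern.** A programmer who follows Section 9.2.1 literally would keep Population 2 gliomas in the co-primary analysis. Nothing downstream removes them. Section 8.1.1 has all imaging studies read by three physicians blinded to history, each of whom must call a lesion recurrence or TRC, so a Population 2 scan would receive a positive or negative call.

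What the reference standard would then record is not defined:
- If the Truth Panel codes tumour found at surgery as positive, the patient becomes TP or FN and enters sensitivity.
- If recurrence is held not to be confirmed, a positive read becomes FP under Section 8.1.3.1 and a negative read counts as a true negative, so the patient enters specificity. (I take FN and TN in the sense that the formulas in Section 8.2.2 need.)
- A lesion recorded by only one of the two evaluations, after both were made, has the other set to negative, which also leads from a positive read to FP.

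At stake are both co-primary estimates, the predictive values, accuracy and misclassification rate, and the meaning of N=118. If the choice stays open, it could be made after the reads are known.

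**Working it through.** **Inputs**
- Planned enrolment: 150 in Population 1, 49 in Population 2 (Abstract).
- Population 1 split: 62 metastatic, 68 high-grade glioma, 20 low-grade glioma (Section 9.1.2, the calculation before version 2.1). 62 + 68 + 20 = 150, and 68 + 20 = 88 gliomas. Version 2.1 does not restate the split.
- Prevalence of recurrence: 0.50 (Section 9.1.1). The alternative of 0.70 is the high-grade figure in Section 9.1.2, applied here to all gliomas.
- Expected sensitivity 0.81 and specificity 0.79; nulls 0.70 and 0.68; lower limit of the 95% Wilson interval (Section 9.1.1).
- Assumed, not in the documents: how Population 2 is coded, and the rate at which its scans are read positive.

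**The plan's own figure.** N=118 at prevalence 0.50 means 59 positives and 59 negatives. The rule described in Section 9.1.1, computed with exact binomial probabilities, first reaches 80% power at 120 positives and at 126 negatives. The larger gives 126 / 0.50 = 252, so 118 is not reproduced. With 59 per class, power is 0.42 for sensitivity and 0.40 for specificity. That is a separate matter; here 118 serves only as the stated target.

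**Which patients count toward 118.** Population 1 gliomas: 88, which is 118 − 88 = 30 short. With Population 2: 88 + 49 = 137, above 118. The documents do not say which count is meant.

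**Share of the sensitivity denominator if all 49 are coded positive.** Share = 49 / (49 + Population 1 gliomas × prevalence).

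| Population 1 gliomas | Prevalence 0.50 | Prevalence 0.70 |
|---|---|---|
| 88 (initial split) | 49/93 = 53% | 49/110.6 = 44% |
| 118 | 49/108 = 45% | 49/131.6 = 37% |
| 69 (if 118 includes the 49) | 49/83.5 = 59% | 49/97.3 = 50% |

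With 88 gliomas the share exceeds one half only if prevalence is below 49/88 = 0.557. Apparent prevalence at 88 and 0.50 would rise from 50% to 93/137 = 68%.

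**Chance that one reader passes sensitivity** (44 Population 1 positives). Alone, the Wilson lower limit exceeds 0.70 from 37 of 44 upward. Pooled, it does so from 74 of 93 upward. The pooled chance is P(X + Y ≥ 74), with X binomial (44, Population 1 sensitivity) and Y binomial (49, r), where r is the assumed Population 2 positive-read rate.

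| Population 1 sensitivity | Population 1 alone | r = 0.60 | r = 0.70 | r = 0.80 | r = 0.90 |
|---|---|---|---|---|---|
| 0.70 (null) | 2.6% | 0.1% | 2.6% | 20% | 66% |
| 0.81 (planned) | 38% | 2.2% | 20% | 65% | 96% |

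**If the 49 are instead coded negative.** With 44 Population 1 negatives at specificity 0.79, expected pooled specificity is (44 × 0.79 + 49 × (1 − r)) / 93. At r = 0.60 this is (34.76 + 19.6)/93 = 0.58. At r = 0.90 it is (34.76 + 4.9)/93 = 0.43. Both lie below the 0.68 threshold.

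**The case against.** The strongest reply is that the rest of the plan makes the intended set clear. The objective, the readers' task and the CSOT categories all concern recurrence against TRC. The sample size assumes a prevalence of recurrence, which has no meaning before treatment. Population 2 has only an exploratory grading aim. On that view no sensible analyst would pool.

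This stands as evidence of intent, and a reader who infers that the sponsor plans to pool the two populations goes beyond the text. It does not cure the definition. The sentence that determines the dataset says otherwise, the sections that use it add no limit, and the MRI analysis shows that the limit could have been written.

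A reader might also infer that sensitivity would be dominated by Population 2, or inflated by it. The documents support neither. No rule codes an untreated tumour as positive. Even if all 49 were so coded, they are a minority in three of the six scenarios above. The 88 comes from the superseded calculation. The direction turns on an assumed read rate.

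Finally, the pass chances concern one reader and one endpoint. Study success in Section 9.2.2 requires both endpoints for the same two of three, so a false pass on sensitivity is not by itself a false study success.

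**Conclusion.** The point holds as a defect in the definition of the primary analysis set. Followed literally, Section 9.2.1 brings patients with neither recurrence nor TRC into the co-primary and secondary estimates, without saying how they are to be scored. This needs correction before the reads are analysed, because the result depends on it.

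The size is conditional. The 37% to 59% share assumes that all 49 Population 2 patients have glioma and are coded positive. The 0.1% to 66% range further assumes 44 Population 1 positives and positive-read rates of 0.60 to 0.90. Under the opposite coding the damage falls on specificity. Confidence is high that the restriction is missing. The direction and amount of any bias cannot be determined from the documents.

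**What to change.** In the efficacy-dataset sentence of Section 9.2.1, describe the patients as *all Population 1 glioma patients (previously treated, with suspected recurrence)*. Leave the rest of the sentence unchanged, including the per-protocol condition and the exclusion of repeat scans, and keep the rule on unreadable scans. Add that Population 2 is analysed only under exploratory objective 5. In Section 9.1.1, state that N=118 refers to Population 1 gliomas and give the planned Population 1 glioma count beside it.

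The wording change is one sentence, and if Population 1 was always intended it alters nothing scientifically. The real cost is disclosure. On the initial split the count is 88 against 118, a shortfall of 30. With 44 positives and 44 negatives, power per reader under the stated rule is 0.385 for sensitivity and 0.405 for specificity. The sponsor must either restate the evaluable number and power on that basis or show an updated glioma count within the 150, which may mean revisiting the planned split.
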